4.1 Device Receipt

IntuiTap Medical will ship devices directly to the clinical sites, to the attention of the Investigator or designee at that site. Device receipt and inventory procedures will be determined by the individual sites' standard operating procedures. At a minimum, a device inventory log will record device serial numbers for reusables and disposables, date of receipt, and disposition. At least two sets of reusable VerTouch components will be provided to each clinical setting within each site.

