6.1 Overview of Study Design

After Informed Consent is obtained, subjects will be randomized 1:1 into two groups via the block randomization method with a list held in each test setting. Standard landmarking techniques will be used in both groups to identify the procedure area. For subjects randomized to the tactile-imaging group (T), VerTouch will be used to identify an interspinous space and to place a marker, introducer, or needle. For subjects randomized to the palpation group (P), the palpation-landmarking method will be used. After marker, introducer, or needle placement, the procedure will continue in the usual manner for subjects in both groups (**Figure 6**).

A designated study observer within each setting will record the time to identify an insertion site; time to place the marker, introducer, or needle; number of insertions, re-directions, and bone contacts (counted until confirmation of spinal canal access

can be assessed); incidence of procedure success; subject's level of discomfort during landmarking; and provider's level of confidence with the identified insertion site. Total procedure time, incidence of traumatic taps, and incidence of referrals to radiology or pain management will be recorded in all settings. In anesthesiology, incidences of paresthesia, unintended dural puncture, and conversion from spinal to epidural anesthesia, will be collected for exploratory analysis, where applicable. Any usability issues or device malfunctions observed during the clinical study will also be documented.

[figure not shown]

Figure 5. Overall Study Design

Although spinal punctures in all clinical settings involve the same localization and insertion processes, there may be variations in setting, subject, and/or provider characteristics. While early VerTouch testing has not evidenced any corresponding variations in device usability and/or outcomes associated with these variations, the study is designed to capture them.

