Accordingly, EM, neurology, and anesthesiology settings will be approximately evenly represented in the study, with at least 24 subjects enrolled in each. To adequately represent patients undergoing obstetric and orthopedic procedures, enrolled anesthesiology subjects will be approximately evenly split between these sub-settings. The PM setting will not be included in the study, as there are limitations, particularly with respect to reimbursement, for ESIs performed with palpation or other non-fluoroscopic techniques. However, PM providers will be represented in IntuiTap's summative usability study, and undergo the same

anesthesiology training as those clinical study investigators specialized in obstetrics and orthopedics.

Additionally, investigators will form a representative sample of typical neuraxial procedure providers, including MDs (residents, fellows, and attendings), PAs, and CRNAs, where applicable. Residents must be in their second post-graduate year and above, having performed at least 5 neuraxial procedures in the past 12 months, and are considered trainees. Apart from their level of training, investigators should have a representative range of relevant experience, indicated by the approximate number of neuraxial procedures they have performed in the past year. To ensure adequate user variability, a single investigator should perform no more than 20% of procedures in his/her setting (corresponding to a minimum of approximately 6 procedures per investigator). Any provider type not included in the study will have been assessed in formative and/or summative human factors testing.

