7.3 Randomization Scheme

Qualifying subjects will be randomized 1:1 via a block randomization scheme to either the tactile-imaging group (T) or the palpation group (P) within each setting (e.g. EM, neurology, or anesthesiology).

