7.4 Clinical Procedures

7.4.1 Visit 1

Screening

At the screening visit the following activities and information will be collected:

- Informed Consent
- Physical Examination (height/weight)
- Eligibility Determination
- Randomization and Subject ID Assignment

- Demographics (gender, age, race, ethnicity)
- Relevant Medical History
- Concomitant Medications

At Treatment

At the time of treatment, the following activities and information will be collected:

- Concomitant Medications
- Pain and/or anti-anxiety medication(s) given for the procedure
- Provider level of training (e.g. resident, fellow, attending, PA, CRNA, NP)
- Provider number of years of in practice
- Provider experience (i.e. number of neuraxial procedures performed in the past 12 months)
- Provider specialty (i.e. emergency medicine, neurology, anesthesiology)
- Procedure setting (i.e. emergency medicine, neurology, orthopedic anesthesiology, obstetric anesthesiology)
- Type of neuraxial procedure (i.e. diagnostic LP, therapeutic LP, spinal anesthesia, epidural anesthesia, CSE, blood patch)
- Reason for Neuraxial Procedure (if not diagnostic LP or blood patch), such as:
 - Therapeutic LP: CSF drainage, intrathecal injection, other
 - Orthopedic procedure: total hip replacement, total knee replacement, other
 - Obstetric procedure: labor/induction, cesarean section, hysterectomy, tubal ligation, other

The subject will be treated with the device or control, per **Figure 6** below (see IFU for more detailed VerTouch steps)^[24]. Initial landmarking for vertebral level is performed by standard technique in both groups in order to identify a safe level when placing the drape to expose the procedure area.

Listed data will be recorded in source documentation, by a member of the study team designated as an observer, as they become available. The observer will also be responsible for counting needle insertions and redirections. Note that procedure success may be reported at different points within the treatment, depending on when spinal access can be confirmed for the particular neuraxial procedure.

[figure not shown]

Figure 6. Flowchart of Visit 1 treatment.

Post-Treatment

After the completion of the procedure, the following activities and information will be collected:

- Patient position (seated, lateral decubitus)

- Length, gauge, bevel (cutting, non-cutting), and type (straight, curved) of needle used

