8.2.1 Adjustments for Multiplicity

The study has a single primary endpoint needed for the superiority analysis. If that analysis reaches statistical significance, then the following additional hypothesis of the secondary variables will be considered sequentially such that if one analysis is statistically significant, then the next hypothesis can be evaluated to control for the Type I error for these analyses:

Additional Hypothesis 1: The null hypothesis that the binary rate of first-attempt success is the same in both groups will be analyzed using a likelihood ratio test ($H_0: p_1 = p_2$ vs $H_1: p_1 \neq p_2$ where p_1 is the success rate in VerTouch subjects and p_2 is the success rate in control subjects). The results will be considered statistically significant if the two-sided p-value is less than 0.05 and the VerTouch success rate is higher than the control rate).

Additional Hypothesis 2: The null hypothesis that the mean number of redirections is the higher in the VerTouch subjects compared to the control group using a T-test with unequal variance assumption ($H_0: \mu_1 \geq \mu_2$ vs $H_1: \mu_1 < \mu_2$ where μ_1 is the mean in VerTouch subjects and μ_2 is the mean in control subjects). The results will be considered statistically significant if the one-sided p-value is less than 0.025.

Additional Hypothesis 3: The null hypothesis that the mean number of passes is the higher in the VerTouch subjects compared to the control group using a T-test with unequal variance assumption ($H_0: \mu_1 \geq \mu_2$ vs $H_1: \mu_1 < \mu_2$ where μ_1 is the mean in VerTouch subjects and μ_2 is the mean in control subjects). The results will be considered statistically significant if the one-sided p-value is less than 0.025.

Additional Hypothesis 4: The null hypothesis that the binary rate of first-pass success is the same in both groups will be analyzed using a likelihood ratio test ($H_0: p_1 = p_2$ vs $H_1: p_1 \neq p_2$ where p_1 is the success rate in VerTouch subjects and p_2 is the success rate in control subjects). The results will be

considered statistically significant if the two-sided p-value is less than 0.05 and the VerTouch success rate is higher than the control rate).

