8.2.2 Primary Effectiveness Analysis

The study is designed to evaluate whether the use of the VerTouch device is able to reduce the number of insertion attempts to successfully access the spinal canal in a spinal puncture as compared to the conventional palpation technique. The primary hypothesis test will be performed by a bootstrap analysis resampling the cases in each group. The null hypothesis for the analysis is:

$$H_0: \mu_1 \geq \mu_2 \text{ vs } H_1: \mu_1 < \mu_2$$

Where μ_1 is the mean attempts in the VerTouch group and μ_2 is the mean for palpation.

This hypothesis will be evaluated using a bootstrap analysis with a one-sided 0.025 test to indicate statistical significance. The results will be presented for the difference in means and the associated 95% CI; and the ratio of the VerTouch mean divided by the palpation mean and the associated 95% CI.

The primary analysis will include the total insertions for each subject regardless of success on the final placement attempt.

The following supporting analyses will be performed:

- The primary analysis will be performed only for subjects who had a procedure success.
- If there are missing data, best- and worst-case imputation analyses will be performed. For the worst-case imputation, the highest observed value will be imputed in the VerTouch group and the lowest value in the palpation group. The best-case analysis reverses the pattern of imputations.
- A Wilcoxon rank-sum test will be used to evaluate the null hypothesis that median attempts are the same in both arms using a two-sided test with a p-value less than or equal to 0.05 considered significant.
- Homogeneity of the log-transformed count results will be assessed using an ANOVA with site, treatment, and site-treatment interaction terms. A p-value for the site-treatment interaction of less than or equal to 0.15 will be considered statistically significant for this analysis. The n, mean, and SD of values by study site will be provided by treatment group.
- The observed attempts will be evaluated through a t-test for unequal variances comparing the difference in the log (insertion attempts) for each group. The difference will be transformed with the exponent function to provide the ratio of the geometric mean attempts and a two-sided 95% CI for the ratio.

The following subgroups will be considered in exploratory covariate analyses:

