2.2 Changes to Planned Analyses

This is the initial version of the statistical analysis plan.

3 Study Objectives

The primary objective of this study is to establish the superiority of VerTouch versus the conventional palpation technique for the number of needle insertion attempts required in diagnostic and therapeutic neuraxial procedures.

4 Investigational Plan and Study Design

Subjects will be randomized 1:1 into two groups via the block randomization method with a list held in each test setting. Standard landmarking techniques will be used in both groups to identify the procedure area. For subjects randomized to the tactile-imaging group (T), VerTouch will be used to identify an interspinous space and to place a marker, introducer, or needle. For subjects randomized to the palpation group (P), the palpation-landmarking method will be used. After marker, introducer, or needle placement, the procedure will continue in the usual manner for subjects in both groups.

The study observer within each setting will record the time to identify an insertion site; time to place the marker, introducer, or needle; number of insertions, re-directions, and bone contacts (counted until confirmation of spinal canal access can be assessed); incidence of procedure success; subject's level of discomfort during landmarking; and provider's level of confidence with the identified insertion site. Total procedure time, incidence of traumatic taps, and incidence of referrals to radiology or pain management will be recorded in all settings. In anesthesiology, incidences of paresthesia, unintended dural puncture, and conversion from spinal to epidural anesthesia, will be collected for exploratory analysis, where applicable. Any usability issues or device malfunctions observed during the clinical study will also be documented.

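### Randomisation is blocked within clinical setting but all eight confirmatory tests pool over setting; a minor loss of precision, immaterial at the planned difference where it can be checked

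*Protocol*

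**What the plan says.** Setting is part of the allocation. SAP section 4 states: "Subjects will be randomized 1:1 into two groups via the block randomization method with a list held in each test setting". Protocol 7.3 says allocation is made "within each setting (e.g. EM, neurology, or anesthesiology", and Protocol 6.1 asks for roughly even representation of the three settings, "with at least 24 subjects enrolled in each".

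The confirmatory analysis does not use it. For the primary endpoint, Protocol 8.2.2 says: "The primary hypothesis test will be performed by a bootstrap analysis resampling the cases in each group". SAP 8.3.3.2 repeats the one-sided 0.025 level and adds nothing on strata, interval type or ties. In Protocol 8.2.1 and SAP 8.2, Additional Hypotheses 1, 4 and 7 are unstratified likelihood ratio tests (of the first of these the protocol says: "The null hypothesis that the binary rate of first-attempt success is the same in both groups will be analyzed using a likelihood ratio test"). Hypotheses 2, 3, 5 and 6 are two-sample unequal-variance t-tests.

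Among the supporting analyses, the homogeneity ANOVA uses site. Provider specialty has the same three levels as setting, but it enters only the one-at-a-time ANOVA on log attempts (SAP 8.3.3.4), which the protocol treats as exploratory.

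**The concern.** Blocking within setting makes the arms alike in setting mix, so differences between settings add almost nothing to the true sampling variance of the treatment difference. A test that pools each arm still counts them in its standard error. If settings differ, the estimated standard error is larger than the design requires, intervals are too wide, and the error rate depends on a between-setting spread that nobody has stated.

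Precision and a predictable error rate for the primary and the seven gated tests are at stake. Bias is not. First-insertion success deserves a look of its own because the six later hypotheses can be tested only if it succeeds.

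**Working it through.** **Inputs.** From Protocol 6.4.1 and SAP 5: 48 per arm; palpation mean 2.1, SD 1.5; VerTouch mean 1.1, SD 0.6; first-attempt success 50% v 81%, stated power 90%. Even settings give 96/3 = 32 per setting, so 16 per arm per setting. Assumed, because the documents give no figures by setting: the palpation setting means below, and a true difference of 0.6 to see power away from its ceiling.

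**1. The plan's own figures.** First-insertion success, with mean rate (0.50 + 0.81)/2 = 0.655:

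Φ{[0.31 − 1.96·√(2·0.655·0.345/48)] / √[(0.25 + 0.1539)/48]} = Φ[(0.310 − 0.190)/0.0917] = Φ(1.31) = 0.904.

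Exact enumeration of the likelihood ratio test gives 90.8%, so the stated 90% is reproduced. For the primary at 48 per arm, SE = √[(2.25 + 0.36)/48] = 0.233 and Φ(1.0/0.233 − 1.96) = 0.990. The plan states primary power only at 24 per group: 89% for the t-test and at least 92% for the bootstrap. A simulation from the same kind of mixture gave 87.8% and 89.0%; the plan does not give its mixture parameters.

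**2. Excess in the pooled standard error.** Under the null, the pooled SE carries the total variance of 2.25. The stratified SE carries 2.25 − σ_b², where σ_b² is the mean of (setting mean − 2.1)².

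| Palpation setting means | σ_b² | √[2.25/(2.25 − σ_b²)] |
|---|---|---|
| 2.1/2.1/2.1 | 0 | 1.00 |
| 1.8/2.1/2.4 | (0.09+0+0.09)/3 = 0.06 | √(2.25/2.19) = 1.014 |
| 1.5/2.1/2.7 | (0.36+0+0.36)/3 = 0.24 | √(2.25/2.01) = 1.058 |
| 1.3/2.1/2.9 | (0.64+0+0.64)/3 = 0.427 | √(2.25/1.823) = 1.111 |

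**3. One-sided type I error, nominal 0.025.** Counts were simulated as 1 + negative binomial. Ranges cover separate runs and variance models and, for the bootstrap, the ways of counting resampled differences of exactly zero.

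| Setting means | Pooled Welch | Stratified t | Planned bootstrap, read as percentile |
|---|---|---|---|
| 2.1/2.1/2.1 | 0.021-0.026 | 0.022-0.026 | 0.025-0.033 |
| 1.8/2.1/2.4 | not reported | not reported | 0.0245-0.029 in one run, 0.031-0.037 in another |
| 1.5/2.1/2.7 | 0.017-0.019 | 0.023-0.024 | 0.021-0.027 |
| 1.3/2.1/2.9 | 0.011-0.016 | 0.021-0.025 | 0.014-0.021 |

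A further repeat at 1.8/2.1/2.4 agreed with the lower run. On either run the percentile bootstrap is not conservative there.

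**4. Power at an assumed difference of 0.6** (setting means equal / 1.5-2.7 / 1.3-2.9).
- Pooled Welch to stratified t: −0.4 to −0.5 / +2.7 to +3.4 / +5.4 to +5.8 points.
- Percentile bootstrap to stratified t, under two variance models: 72.1 to 69.1% and 65.1 to 63.1% / 72.7 to 72.9% and 67.8 to 69.4% / 73.1 to 75.9% and 70.7 to 74.8%. Over tie rules the changes are about −5 to −1 / −2 to +2 / 0 to +5 points.
- With equal means, 2.6 of the 3.0 points and 1.5 of the 2.0 points lost come from removing the percentile interval's excess error.

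**5. At the planned values.** Primary power is about 98-100% with either analysis. For first-insertion success (likelihood ratio to Cochran-Mantel-Haenszel), by assumed palpation rates:
- 50/50/50: 90.8 to 90.4% (−0.4)
- 60/50/40: 91.2 to 91.2% (0)
- 65/50/35: 91.4 to 91.9% (+0.5)
- 75/50/25: 92.3 to 94.2% (+1.9)

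A separate run at 80/50/20 gave 93.2 to 95.8% (+2.6).

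**The case against.** The strongest reply is that this is a preference about efficiency. Blocking for balance and then testing without strata is valid, every gain above rests on assumed spreads, and Protocol 6.1 reports that "early VerTouch testing has not evidenced any corresponding variations in device usability and/or outcomes". If settings do not differ, the change loses a little power. Much of this stands and is why the point is minor. Two limits apply: the early-testing statement concerns the device and not palpation, and the same section allows that settings may vary.

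A reader might infer that the planned tests are simply conservative. That is too general for the primary. If the unnamed bootstrap is a percentile interval, it is slightly liberal by itself, and the two effects roughly cancel at moderate spreads.

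A reader might also infer that the stratum is contradictory, because Protocol 7.4.1 records "Procedure setting (i.e. emergency medicine, neurology, orthopedic anesthesiology, obstetric anesthesiology" while 7.3 lists three settings. Protocol 6.1 treats obstetrics and orthopedics as sub-settings of anesthesiology, which largely answers this. The line in Protocol 4.1, "At least two sets of reusable VerTouch components will be provided to each clinical setting within each site", is about device supply and does not show that lists are kept per site. That one question remains open.

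Finally, the provider-specialty ANOVA will give a near setting-adjusted estimate. It does, but on the log scale and outside the confirmatory tests.

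**Conclusion.** The point holds as a minor improvement. No confirmatory test uses the factor within which subjects are randomised. If outcomes differ by setting, the pooled standard error is larger than needed, by about 1%, 6% or 11% for the three assumed spreads. This moves the tests towards conservatism and does not inflate type I error. Read as percentile, the planned bootstrap is clearly conservative only when settings differ widely.

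The documents do not support the stronger inferences that the primary result is at risk or that power is materially lost. At the planned difference the effect on the primary and on Hypothesis 1 is immaterial. That reassurance is tied to the planned values: at a difference of 0.6 with wide spreads, the like-for-like gain from stratifying is 5 to 6 points. Hypotheses 2 to 7 have no planned difference, so nothing can be said about their power.

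**What to change.** In Protocol 8.2.1-8.2.2 and SAP 8.2 and 8.3.3.2, analyse by the stratum used for the randomisation lists.

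- **Primary.** Estimate Σ w_s·(difference in setting s), where w_s is the setting's share of all subjects, with SE = √{Σ w_s²·(s²_V/n_V + s²_P/n_P)} computed within settings. Test against a Satterthwaite t at one-sided 0.025, and form the ratio of means from the same setting-weighted means. Alternatively keep the bootstrap, resampling within treatment-by-setting cells with a symmetric studentised interval (simulated error 0.020-0.025). Do not use a within-cell percentile interval (0.028-0.036 across runs).
- **Binary secondaries.** Use Cochran-Mantel-Haenszel by setting, in exact form where the plan's small-cell rule would call for Fisher's test.
- **Mean secondaries.** Use a linear model with treatment and setting and robust standard errors.
- **Sensitivity.** Keep the planned pooled tests.
- **Clarify.** State whether the lists are also kept per site.

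The cost is wording and a little code before the analysis; setting is already recorded. If setting is not prognostic, the like-for-like loss at a difference of 0.6 is about 0.5 point of power. Against a percentile bootstrap it is about 2-3 points (about 1-5 over tie rules), mostly from removing that interval's liberal error. The studentised bootstrap gives up a further 1-3 points against the Satterthwaite test.

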8.2.3 Additional Analyses

The tertiary and exploratory endpoints will be summarized descriptively. Tertiary endpoints of localization time, insertion time, and number of bone contacts will also be evaluated for homogeneity of the group results using a Mann-Whitney test. The exploratory endpoint of procedure time will also be evaluated with a Mann-Whitney test. The tertiary, safety, and exploratory incidence endpoints will be evaluated for homogeneity of the rates across the treatment groups using likelihood ratio tests.

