6.3.4 Safety Endpoints

1. Incidence of post-dural puncture headache (PDPH)
2. Incidence of unintended dural puncture (specific to epidural anesthesia)
3. Incidence of paresthesia during needle insertion (specific to neuraxial anesthesia)
4. Incidence of traumatic tap (results in visible blood aspiration)

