9.3 Anticipated Adverse Events

Anticipated adverse events are outlined below, with control rates listed separately as reported in the literature on LPs and neuraxial anesthesia. Few adverse events are associated with insertion attempts, and with the exception of unintended dural puncture, none have been directly tied to insertion depth (if performed at the correct vertebral level, below the cauda equina). It is important to note that the various risk factors associated with nearly all of these complications lead to great variability in reported rates. In particular, the incidence of most adverse events that can be linked to number of insertion attempts is directly correlated with needle characteristics, such as size and shape^[8]. Additionally, rare complications have been found to be associated with the presence of spinal deformities, which are study exclusions^[34,35].

Adverse events associated with LPs include^[41]:

- PDPH, 40% (important risk factors include needle size and shape, use of stylet, patient position, number of attempts, and volume of CSF removed; may lead to the need for further treatment, including epidural blood patch)^[42]
- Cranial neuropathy, 0.4%
- Paresthesia (nerve root irritation), 13%^[43]
- Low back pain, 35%
- Bacterial meningitis, 0.2%
- Intracranial bleeding, rare
- Traumatic lumbar puncture, up to 72%, with 15.6% reported for cutoff of 400 erythrocytes/ μ L in the first tube (in laboratory analysis, may lead to false-positive diagnosis of SAH or other cerebral vascular malformations)^[43,44]
- Retroperitoneal abscess, rare^[45]
- Spinal hematoma, rare

Adverse events associated with neuraxial anesthesia include the following (rates are mostly reported for epidural anesthesia; where not specific to an epidural, rates are higher with spinal and combined spinal-epidural anesthesia)^[46,47]:

- Unintended dural puncture, 1.5%
- Post-dural puncture headache, 0.21-1.5%
- Spinal abscess, 0.0002%
- High spinal block, 0.002%
- Paresthesia (transient neurologic injury), 0.018%^[9]
- Spinal hematoma, 0.0002%

- Hypotension (requiring treatment), 30%
- Persistent neurologic injury, 0.0004%^[9]
- Permanent neurological injury, 0.001%
- Inadequate analgesic effect (failure), 6.3%
- Pruritus, 12%
- Backache, 12%
- Nerve damage caused by needle trauma, 0.0006%
- Epidural abscess, 0.003%
- Bacterial meningitis, 0.003%
- Epidural hematoma, 0.0006%
- Fetal heart rate abnormalities: 5.5%
- Fetal bradycardia: 4.7%

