8.3.3.4 Covariate and Other Supporting Analyses

The ANOVA model based on the log(attempts) will consider each of the following covariates one at a time with the factor, treatment, and factor-treatment interaction. The n, mean, and standard deviation (SD) of values for the number of attempts by factor levels will be provided by treatment group. Subgroup levels will only be considered if there are at least 8 subjects within the covariate level across both treatments. The covariates to be analyzed are:

- BMI (kg/m²): underweight (<18.5), normal (18.5-24.9), overweight (25-29.9), class 1 obesity (30.0-34.9), class 2-3 obesity (≥ 35 .0)
- Age (year): adolescent (<22), young adult (22-40), middle-aged adult (41-65), older adult (>65)
- Provider type: MD, PA, CRNA, AA, NP
- Provider specialty: emergency medicine, neurology, anesthesiology
- MD level (MDs only): resident, fellow, attending
- Provider years in practice: <5, 5-10, >10
- Provider experience (number of neuraxial procedures in past 12 months): 5-25, 26-50, 51-100, >100
- Neuraxial procedure: diagnostic LP, therapeutic LP, neuraxial anesthesia, blood patch
- Medication given for procedure: none, pain, anti-anxiety
- Needle type: spinal 20-22G cutting, spinal 20-22G non-cutting, spinal >22G, Tuohy, CSE
- VerTouch workflow (VerTouch subjects only): marking, introducer placement, needle placement

Statistical Analysis Plan

Client/Project	IntuiTap/VerTouch
Version and Date	V02 – 22 December 2020

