8.3.6 Safety Endpoints

The following safety related endpoints were identified in the protocol:

- Incidence of post-dural puncture headache (PDPH)
- Incidence of unintended dural puncture (specific to epidural anesthesia)
- Incidence of paresthesia during needle insertion (specific to neuraxial anesthesia)
- Incidence of traumatic tap (results in visible blood aspiration)

These would be analyzed as binary endpoints and compared with likelihood ratio chi-squared tests.

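### Post-dural puncture headache is compared between arms in one unstratified test with no planned breakdown by procedure, although the protocol's expected rates for lumbar puncture and neuraxial anesthesia are far apart

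*Protocol*

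**What the plan says.** Protocol 6.3.4 lists "Incidence of post-dural puncture headache (PDPH") with no limit by procedure. The next item in the same list is limited: "Incidence of unintended dural puncture (specific to epidural anesthesia").

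The planned comparison in Protocol 8.2.3 is: "The tertiary, safety, and exploratory incidence endpoints will be evaluated for homogeneity of the rates across the treatment groups using likelihood ratio tests". SAP 8.3.6 says of the four safety endpoints: "These would be analyzed as binary endpoints and compared with likelihood ratio chi-squared tests". No stratification factor is named in either place.

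Procedure type is a planned factor only for the primary endpoint. SAP 8.3.3.4 opens: "The ANOVA model based on the log(attempts) will consider each of the following covariates". The matching list in Protocol 8.2.2 stands under the primary effectiveness analysis. Adverse events are summarized overall and by relatedness, seriousness and severity (Protocol 8.2.4, SAP 8.3.7), not by procedure.

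Protocol 9.3 gives anticipated events "with control rates listed separately as reported in the literature on LPs and neuraxial anesthesia". The LP list has "PDPH, 40% (important risk factors include needle size and shape". The anesthesia list has "Post-dural puncture headache, 0.21-1.5" percent. Its lead-in says that these rates are mostly epidural and that events not specific to epidurals are more frequent with spinal and combined spinal-epidural anesthesia.

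Protocol 7.3 randomizes 1:1 in blocks within each setting. Protocol 6.1 asks for roughly equal representation of emergency medicine, neurology and anesthesiology, with at least 24 subjects in each.

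**The concern.** On the protocol's own figures, nearly all expected PDPH events come from LP subjects. The anesthesiology third adds subjects to each arm's denominator but almost no events.

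This has two consequences. First, one incidence per arm describes neither population: it is too low for LP and too high for anesthesia, and it changes with the enrolled mix even when no true rate changes. Second, an unstratified test counts the variation between procedures as noise, although randomization within setting has largely balanced it between arms. For a safety endpoint this matters because the test becomes less able to show an excess of headaches with the device.

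**Working it through.** **Check of the method.** The documents state no power for PDPH. Their one binary power figure is 90% for first-attempt success, 50% v 81% with 48 per arm (Protocol 6.4.1). Exact enumeration of the likelihood ratio test at two-sided 0.05 gives 90.8%, so the figure is reproduced.

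**Inputs.**
- 96 subjects, 48 per arm (Protocol 6.4.1).
- At least 24 per setting (Protocol 6.1). Anesthesiology can therefore have 24 to 96 − 24 − 24 = 48 subjects; an even split gives 32.
- PDPH 40% for LP and 0.21–1.5% for anesthesia (Protocol 9.3).
- Two-sided 0.05 (Protocol 8.2).

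**Assumptions.** Emergency medicine and neurology subjects have LP, as in Protocol Table 1. Anesthesiology subjects have neuraxial anesthesia, with no blood patches. Arms are balanced within setting.

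**Gap between the rates.** 40/1.5 = 26.7 and 40/0.21 = 190. If the anesthesia rate with spinal cases included were 3%, 5% or 10% (assumed), the ratio would be 13, 8 or 4.

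**Pooled incidence.** With L LP subjects and anesthesia rate r, the expected value is (L × 0.40 + (96 − L) × r)/96:

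| LP + anesthesia | r = 0.21% | r = 1.5% |
|---|---|---|
| 72 + 24 | 30.1% | 30.4% |
| 64 + 32 | 26.7% | 27.2% |
| 48 + 48 | 20.1% | 20.8% |

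At 64 + 32, expected events are 64 × 0.40 = 25.6 in LP and 32 × 0.0021 = 0.07 to 32 × 0.015 = 0.48 in anesthesia.

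**Why the pooled test is conservative.** Take 32 LP + 16 anesthesia per arm, no difference between arms, and r = 1.5%.
- Variance used by the pooled test: 2 × 0.2717 × 0.7283/48 = 0.00824.
- Actual variance with procedure balanced: (2/3)² × 2 × 0.40 × 0.60/32 + (1/3)² × 2 × 0.015 × 0.985/16 = 0.00687.
- The standard error is too large by √(0.00824/0.00687) ≈ 1.095.

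Exact null rejection of the pooled likelihood ratio test is 3.6%. A Cochran-Mantel-Haenszel (CMH) test without continuity correction rejects 5.3%. With LP at 20%, the pooled test rejects 4.9%, so the conservatism depends on the LP rate.

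**Power at 32 + 16 per arm.** The pooled test was enumerated exactly and CMH simulated (1,000,000 runs). All differences between arms are assumed.

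| LP rates | Anesthesia rate, both arms | Pooled | CMH |
|---|---|---|---|
| 40% v 65% | 1.5% | 38% | 52% |
| 40% v 65% | 5% (assumed) | 38% | 48% |
| 40% v 65% | 10% (assumed) | 38% | 46% |
| 40% v 20%, or 20% v 40% | 1.5% | 38% | 41% |
| 20% v 40% | 10% (assumed) | 36% | 36% |
| 10% v 25% | 1.5% | 34% | 34% |

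With the same risk ratio in both strata, starting from 40% and 1.5%, pooled v CMH is 27% v 37% at a risk ratio of 1.5 and 83% v 92% at a risk ratio of 2.

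**Harm in anesthesia only.** With 1.5% rising to 20% there (assumed) and LP unchanged, the pooled test has 9% power and CMH 10%.

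**The case against.** Several points on the other side stand.

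- **No bias.** A reader might infer that pooling biases the safety comparison. It does not: blocking within setting keeps case mix nearly equal between arms. The pooled test is valid, and at the quoted rates conservative.
- **Not a lower bound.** A reader might take 27-fold as the minimum gap. The documents do not support that. The smallest quoted ratio is 26.7, the anesthesia rates are mostly epidural, and the trial also includes spinal and combined procedures, for which section 9.3 says rates are higher without giving a figure.
- **The power loss is not general.** It depends on the 40% LP rate and on an increase from it. Section 9.3 itself warns that reported rates vary greatly. For 20% v 40% the loss is about 3 points, and at a 10% LP rate it is about nil.
- **Traumatic tap.** It is tempting to extend the argument to this endpoint, but section 9.3 gives a rate for LP only, so the documents do not show a difference between procedures.
- **No benchmarking is planned.** Nothing says that the observed incidence will be compared with section 9.3; the comparator is randomized palpation.
- **Inference from silence.** SAP section 10 leaves the table list to be completed, and Protocol 8.2 promises listings of all case report form data. A breakdown by procedure is possible; it is simply not committed to.
- **Supportive role.** PDPH has no powered hypothesis and lies outside the sequential testing of Protocol 8.2.1.

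These points limit the size of the concern. They do not remove it: a single PDPH rate remains hard to interpret, and the stratified test is as good or better in the scenarios above.

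**Conclusion.** The point holds as a cheap improvement, not as a fault that invalidates the safety comparison. The plan commits to one unstratified PDPH test and to no rates by procedure, while its own expected rates differ about 27- to 190-fold on the mostly epidural figures quoted.

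The firmer consequence is interpretability: the pooled incidence can shift by about 10 percentage points on case mix alone. This rests on the quoted rates and on treating emergency medicine and neurology subjects as LP.

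The power consequence is conditional. At a 40% LP rate and an assumed rise to 65%, stratification gains about 14 points with anesthesia at 1.5% and about 8 points with anesthesia at an assumed 10%. It gains little or nothing if the LP rate is much lower.

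**What to change.** In Protocol 8.2.3 and SAP 8.3.6:

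1. Report PDPH by arm separately for LP and for neuraxial anesthesia.
2. Put blood patch subjects on their own line and outside the incidence comparison. They are eligible because they already have PDPH, and Protocol 8.2.2 treats blood patch as a separate procedure category.
3. Make the test between arms a Cochran-Mantel-Haenszel test stratified by LP versus neuraxial anesthesia.
4. Keep the pooled incidence as a secondary line.

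The cost is a wording change and one more table. Procedure type is already collected (Protocol 7.4.1), and neither sample size nor randomization changes. The downside is that the anesthesia stratum will have very few events. A common-effect stratified test also adds little if harm occurs only there, which is why the separate rates are needed as well as the test.
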